The only dose finding study of SBRT for lung tumors was reported by Timmerman, et al. from Indiana. They conducted a phase I study of dose escalation of a three fraction regimen, starting with 8 Gy x 3, and escalating to 10, 12, 14, 16, 18, 20 and 22 Gy x 3 fractions, in patients with potentially resectable NSCLC but who were not surgical candidates for medical reasons ("medically inoperable"). Doses were calculated without correction for tissue inhomogeneity. Patients were enrolled into three separate dose escalation groups based on tumor size. While dose-limiting toxicity (DLT) was observed in one or two patients at several dose levels, the protocol-defined maximum tolerated dose (MTD) was only observed in patients with large T2 tumors (5-7 cm in size) at 22 Gy x 3. In other tumor size groups, dose escalation was stopped prior to reaching the MTD (20-22 Gy x 3). Greater than 90% primary tumor control was observed with 20 Gy x 3; this total dose of 60 Gy corresponds to a biologically equivalent dose (BED) [if expressed in 2 Gy/fraction] of 180 Gy if using the formula  $BED = nd(1+d/\alpha/\beta)$ , where  $n$  = number of fractions;  $d$  = dose per fraction; and  $\alpha/\beta = 10$  for acute reacting tissue), although it is not clear how applicable this conversion is to highly hypofractionated treatments.

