Five fractions were chosen because this short, practical schedule is suitable for patients with comorbidities and/or patients traveling from a distance to an SBRT center, as well as being within the definition of SBRT as accepted by regulatory bodies; it has potential radio-biological advantages of the 3 fraction schedule as repair of sub-lethal damage occurs after each fraction. Thus, more repair and greater tolerance of normal structures would be expected, particularly in the penumbra region of the high dose with 5 rather than with 3 fractions.

The MTD for this schedule will be assessed by the adverse events within the first 12 months following study entry. This was felt to be more clinically relevant than the classical 90 day toxicity, as the dose-limiting toxicity of SBRT to central thoracic structures may be acute (within a month of SBRT) but is more likely to be sub-acute (1-6 months post SBRT) and chronic (more than 6 months post SBRT).

The starting RT dose for the study will be 10 Gy x 5 fractions every 2 days, over 1½ - 2 weeks (total dose [TD] of 50 Gy). The subsequent dose levels will escalate dose by 0.5 Gy per fraction (i.e., a 2.5 Gy total dose) to a maximum dose of 12 Gy x 5 fractions (TD 60 Gy in 5 fractions). Several lower dose levels will be employed if unacceptable dose-limiting toxicity (DLT) is seen with the planned starting dose of 10 Gy. All treatment plans will have to respect the organ-at-risk doses as outlined in the protocol and discussed below.

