**Image-Guided Therapy Center (ITC)**

**ATTN: [name]**

**[name]**

**St. Louis, MO 63108**

**[contact]**

**[contact]**

**13.0 STATISTICAL CONSIDERATIONS**

**13.1 Study Endpoints**

**13.1.1** Primary Endpoint of Phase I Portion (7/27/10)

The maximal tolerated dose (MDT) of SBRT radiation dose associated with a 0.20 probability of dose-limiting toxicity (DLT); DLT is defined as any grade 3 or worse toxicity (per CTCAE, v.4, MedDRA, v. 12.0), that occurs within 1 year from the start of SBRT, is possibly, probably, or definitely related to treatment, and is related to the following specific symptoms:

- Grade 3-5 Cardiac Disorders
  - Pericardial effusion
  - Pericarditis
  - Restrictive cardiomyopathy
- Grade 4-5 Gastrointestinal Disorders
  - Dysphagia
  - Esophagitis
  - Esophageal fistula
  - Esophageal obstruction
  - Esophageal perforation
  - Esophageal stenosis
  - Esophageal ulcer
  - Esophageal hemorrhage
- Grade 3-5 Nervous System Disorders
  - Brachial plexopathy
  - Recurrent laryngeal nerve palsy
  - Myelitis
- Respiratory, Thoracic, and Mediastinal Disorders, Grade 3-5, except as noted below
  - Atelectasis (grade 4-5 only)
  - Bronchopulmonary hemorrhage
  - Mediastinal hemorrhage
  - Pleural hemorrhage
  - Tracheal hemorrhage
  - Bronchial fistula
  - Pulmonary fistula
  - Bronchopleural fistula
  - Tracheal fistula
  - Hypoxia (provided grade 3 is worse than baseline)
  - Bronchial obstruction
  - Tracheal obstruction
  - Pleural effusion
  - Pneumonitis
  - Pulmonary fibrosis

- Changes in Pulmonary Function Tests per the SBRT Pulmonary Toxicity Scale (see Section 6.9.5), Grade 3-5
  - FEV1 decline
  - Forced Vital Capacity decline
- Any Grade 5 adverse event attributed to treatment

All reported serious adverse events (SAEs) listed above will be reviewed by 1 of 3 designated senior radiation/medical oncologists who have expertise in the treatment of lung cancer and who are not associated with this study within 2 business days of receipt of all supporting documentation. The determination of those SAEs as a study DLT will be made by the designated independent reviewer. All reported SAEs listed above will be considered DLTs until reviewed by the designated independent reviewer.

**13.1.2** Primary Endpoint of Phase II Portion (8/20/10)

Two-year primary tumor control rate at the MTD of SBRT (See Section 11.3.3)

**13.1.3** Secondary Endpoints

**13.1.3.1** Progression-Free Survival (see Section 11.3.3);

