**13.1.3.2** Overall Survival (see Section 11.3.3);

**13.1.3.3** Local Progression (see Section 11.3.3);

**13.1.3.4** Regional nodal progression (see Section 11.3.3);

**13.1.3.5** Distant metastases (see Section 11.3.3);

**13.1.3.6** Any grade 3 toxicity other than a DLT occurring within the first year;

**13.1.3.7** Late grade 3 toxicity.

**13.1.4** Tertiary Endpoints (Exploratory) [8/20/10]

**13.1.4.1** To study if molecular markers (proteomic or genomic) in the blood circulation will predict 2-year primary tumor control rate, or the occurrence of grade  $\geq 2$  pulmonary adverse events, or the occurrence of grade  $\geq 2$  non-pulmonary adverse events;

**13.1.4.2** To study the prognostic significance of comorbidity status;

**13.1.4.3** To describe the medical physics endpoints of tumor motion and inter-fraction (setup) errors.

**13.2** Justification of Design (7/27/10)

Since this trial will provide an estimate of efficacy for the MTD dose, it can be thought of as a seamless phase I/II trial. Monte Carlo simulation is used to assess the operating characteristics of this trial with respect to each of these metrics in turn. Three simulations were performed for the true dose-conditional probability of toxicity, which are described in Table 13.1. Scenario 1 (DLT-td) is the initial trial design for true dose-conditional probability of toxicity. Scenario 2 (DLT+) is approximately twice as toxic as assumed by the trial design. Scenario 3 is more than twice as toxic as the trial design, with rapidly increasing toxicity at dose Levels 7 and higher (DLT++).

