The distributions of target doses that the trial selects are presented in the right column of Figure 13.1. If the design assumptions about P(DLT) are correct (DLT-td), the trials overwhelmingly pick the correct target dose, indicated by the asterisk (Level 9). If P(DLT) is underestimated as in scenario DLT+ , the target dose is picked within one level of the true target dose (i.e., with  $0.15 \leq P(\text{DLT}) \leq 0.30$ ) in over 90% of the simulated trials. If the P(DLT) is more severely underestimated as in scenario DLT++ , that proportion is higher.

[figure not shown]
**13.2.3** Estimation of Primary Tumor Control (8/20/10)

The average number of patients treated at each dose is displayed in the left column of Figure 13.2. Again, the target dose is denoted by an asterisk. In the DLT-td cases, 7-14 patients are treated at Levels 5-8 due to the starting dose (level 5, 10 Gy) and escalation restrictions. In the DLT+ simulations, 8-14 patients on average are treated on either of the 2 dose levels (8 and 9) with  $P(\text{DLT}) > 0.3$ , which result, on average in 3-5 DLTs. In the DLT++ simulations, 8-15 patients on average are treated on 1 of 3 dose levels (7, 8, and 9) with  $P(\text{DLT}) > 0.3$  which result on average in 4-8 DLTs.

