The goal of the trial is to determine the fraction size (dose) for SBRT most closely associated with a 0.20 probability of a DLT (specified as the *target rate*). As patients present for enrollment, they are assigned the highest dose associated with an estimated probability of a DLT less than or equal to the target rate of 0.2. The initial estimates of the probability of a DLT at each dose (column 3 of Table 13.1) are updated with the accumulated patient information using a Bayesian paradigm so that the estimation of the target dose, and, thereby, the assignment of the next dose, is based upon all the information available at the time of enrollment. To allow the trial to remain open to new patient entries without pause, while using the maximum available information, data from patients who have been enrolled but have not completed the 1 year observation period are weighted according to the proportion of the observation period the patient has completed (data from patients who have experienced a DLT are fully weighted).

**Table 13.1:** Toxicity probability estimates of trial design and simulation assumptions used to determine operating characteristics

Dose Level	SBRT Fraction Dose (Gy)	Probability of Toxicity			
		Design ( $p_0$ )	Scenario		
			DLT per trial design (DLT-td)	DLT+	DLT++
1	8.0	0.01	0.01	0.02	0.02
2	8.5	0.02	0.02	0.04	0.05
3	9.0	0.04	0.04	0.06	0.08
4	9.5	0.05	0.05	0.10	0.13
5	10.0	0.08	0.08	0.15	0.18
6	10.5	0.10	0.10	0.20	0.30
7	11.0	0.14	0.14	0.30	0.40
8	11.5	0.17	0.17	0.35	0.60
9	12.0	0.20	0.20	0.45	0.80

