#### **13.5.1.1 Analysis of Dose-limiting Toxicities (7/27/10)**

The maximal tolerated dose (MTD) of SBRT radiation associated with a 0.20 probability of dose-limiting toxicity (DLT) will be determined as that dose having P(DLT) closest to the target rate of 0.20. DLT is defined as any grade 3 or worse toxicity (per CTCAE, v. 4, MedDRA, v. 12.0), that occurs within 1 year from the start of SBRT, is possibly, probably, or definitely related to treatment, and is related to the specific symptoms in Section 13.1.1). Markov Chain Monte Carlo will be used to estimate the probability of DLT at each dose, along with 95% posterior intervals, using the logistic dose-toxicity model (eg 1) described in Section 13.5.1. The observed proportion of patients experiencing a DLT will be calculated. The distribution of all toxicities will be tabulated by grade and category, as well as the following information:

- I) Analysis by Assigned Dose Level
  - a. Total number of patients assigned to that dose level
  - b. Number of patients who received the assigned dose level
    - i. Number of patients still in treatment
    - ii. Number of patients not evaluable for DLT analysis
    - iii. Number of patients evaluable for DLT analysis
      1. Number of patients who experienced a DLT
      2. Number of patients still at risk for a DLT
      3. Number of patients who completed the risk interval without a DLT
  - c. Number of patients who did not receive the assigned dose level but who received a lower dose level
    - i. Number of patients still in treatment
    - ii. Number of patients not evaluable for DLT analysis
    - iii. Number of patients evaluable for DLT analysis
      1. Number of patients who experienced a DLT
      2. Number of patients still at risk for a DLT
      3. Number of patients who completed the risk interval without a DLT
- II) Analysis by Actual Dose Delivered
  - a. Number of patients still in treatment
  - b. Number of patients not evaluable for DLT analysis
  - c. Number of patients evaluable for DLT analysis
    - i. Number of patients who experienced a DLT
    - ii. Number of patients still at risk for a DLT
    - iii. Number of patients who completed the risk interval without a DLT

In addition, for those patients who did not receive the assigned dose level, the following information will be reported:

1. Dose level actually received
2. Assigned dose level

3. Reason for dose modification

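### The MTD rule has no 'not reached' outcome and the design target sits at the top dose level, so clearly lower toxicity would nearly always be reported as an MTD at Level 9

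*Protocol*

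**What the plan says.** Section 13.1.1 makes the phase I primary endpoint the "SBRT radiation dose associated with a 0.20 probability of dose-limiting toxicity (DLT". Section 13.4.1 gives the goal as the fraction size "most closely associated with a 0.20 probability of a DLT". Section 13.5.1.1 turns this into a selection rule: the MTD "will be determined as that dose having P(DLT) closest to the target rate of 0.20". It also requires the estimated P(DLT) at each dose with 95% posterior intervals and the observed DLT proportion, but ties no conclusion to them.

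Section 1.3 ends the dose range at Level 9: escalation runs "to a maximum dose of 12 Gy x 5 fractions (TD 60 Gy in 5 fractions". Table 13.1, the "Toxicity probability estimates of trial design and simulation assumptions used to determine operating characteristics", sets the design probabilities for Levels 1 to 9 at 0.01, 0.02, 0.04, 0.05, 0.08, 0.10, 0.14, 0.17 and 0.20. Section 13.2.2 confirms that trials simulated under the design curve "pick the correct target dose, indicated by the asterisk (Level 9".

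Section 13.2 tests mis-specification with two alternatives. "Scenario 2 (DLT+) is approximately twice as toxic as assumed by the trial design", and Scenario 3 is more toxic still. The phase II endpoint (Sections 13.1.2, 13.5.1 and 13.5.1.2) is two-year primary tumor control at the MTD.

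The background in Section 1.2 draws the missing distinction for an earlier dose-finding study: "In other tumor size groups, dose escalation was stopped prior to reaching the MTD".

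**The concern.** The endpoint definition and the selection rule agree only when some level has P(DLT) near 0.20. Because the design puts 0.20 at the last level, that holds only if toxicity is about as assumed or worse. If toxicity is clearly lower, the rule still returns an MTD, and it returns Level 9.

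The trial would then report a dose associated with a 0.20 DLT probability when it had found the highest dose it was set up to give. The phase II result would be described as tumor control at the MTD when it is control at the top of the range. The rule has the same gap at the bottom: if every level exceeded 0.20, Level 1 would be closest and would be named the MTD.

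**Working it through.** **Inputs.** Design probabilities p0 from Table 13.1. From Section 13.4.1: d = log(p0/(1-p0)) - 3, p(d) = exp(3+ad)/(1+exp(3+ad)), prior a ~ N(1, SD 0.3), weight u/12. From Section 13.4.2: start at Level 5, at most one level up between consecutive patients, 12 months of cumulative observation at the current level before escalating. From Section 13.3: 75 evaluable patients, 2 per month.

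**The plan's own figures first.** 75/0.80 = 93.75, so 94 entries; 94/2 = 47 months, about 4 years. Both agree with Section 13.3. Re-simulating the design with a flat hazard (500 trials per condition) gave:

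- Design curve: median 11 DLTs; 90% of trials with fewer than 15 (stated: over 85%); 99.6% with fewer than 18 (stated: at least 99%); on average 8 to 13 patients at each of Levels 5-8 (stated: 7-14). Level 9 was selected in 69% of trials and Level 8 in 20%.
- DLT+: Level 6 selected in 41-47% of trials over three hazard shapes (stated: about 40%).

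The early and late hazard shapes had to be assumed because the figure insets are not shown. Under the assumed late shape, 81% and 97% of design-curve trials fell below 15 and 18 DLTs, somewhat under the stated values.

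**The rule applied to the model curve.** For Level 9, d = log(0.20/0.80) - 3 = -1.386 - 3 = -4.386. Then p(Level 9) is 0.20 at a = 1, 0.139 at a = 1.1, 0.094 at a = 1.2, 0.063 at a = 1.3 and 0.027 at a = 1.5. For every a of 1 or more, Level 9 is the highest of nine values at or below 0.20, so it is always closest.

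**How much prior weight lies there.** p(Level 9) < 0.15 needs a > (1.735+3)/4.386 = 1.079; < 0.10 needs a > (2.197+3)/4.386 = 1.185. Under N(1, 0.3) the prior probabilities are 50% for below 0.20, 40% for below 0.15 and 27% for below 0.10. At the bottom, d for Level 1 is -4.595 - 3 = -7.595, so Level 1 exceeds 0.20 only if a < 4.386/7.595 = 0.578, prior probability 8%.

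**With sampling error** (flat hazard, 500 trials each; true curve = multiple of p0; MTD = level whose p at the posterior mean of a is closest to 0.20):

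| True toxicity | True P(DLT), Level 9 | Level 9 reported as MTD | Median estimate, Level 9 | 95% interval wholly below 0.20 |
|---|---|---|---|---|
| Design | 0.20 | 68.6% | 0.197 | 4.4% |
| 0.75x | 0.15 | 91.6% | 0.157 | 19.2% |
| 0.5x | 0.10 | 99.2% | 0.104 | 67.2% |
| 0.25x | 0.05 | 100% | 0.062 | 97.2% |
| 5% at all levels | 0.05 | 99.6% | 0.067 | 92.2% |

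The Monte Carlo standard error at 0.75x is sqrt(0.916 x 0.084/500) = 0.012. Repeat runs gave 93% at 0.75x, 99% or slightly more at 0.5x and 100% at 0.35x. In them the interval lay below 0.20 in about 18% of trials at 0.75x, 63% at 0.5x and 5% at the design truth. Selecting on the posterior mean of P(DLT) instead changes little (90.4% at 0.75x, 98.8% at 0.5x).

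**Coverage of Section 13.2.** The 0.20 point is at Level 9 under the design, at Level 6 under DLT+, and between Level 5 (0.18) and Level 6 (0.30) under DLT++. In all three it lies within the range studied, so the quoted selection accuracy says nothing about a target above it.

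**The case against.** Choosing the closest level is a common CRM rule, Section 13.4.1 words the goal the same way, and the dose cap is disclosed. Section 13.5.1.1 already requires P(DLT) with intervals at every dose, so an estimate of 0.10 at Level 9 would be visible. Dose assignment does not change, and the phase II patients, estimate and null of 0.7 are the same whatever Level 9 is called. The simulated percentages partly restate the rule. Wording for a boundary result could be left to an analysis plan that is not shown.

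Most of this stands and limits the weight of the point. It does not remove it. The protocol itself fixes the selection rule, and following that rule can yield a conclusion that contradicts Section 13.1.1. Visible intervals do not change a conclusion that is not tied to them.

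Four stronger readings are tempting and are not supported:

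- A reader might infer that any less toxic truth always ends at Level 9. That is exact for the rule applied to the true curve, but in realised trials at 0.75x about 7-8% select a lower level.
- A low estimate at Level 9 when the design curve is true is sampling error, not mislabelling; Level 9 is then the right answer.
- Nothing in the protocol suggests that a low rate would be concealed.
- The bottom-end case is a gap in wording and was not simulated. Under Section 13.4.2 no level would then qualify for assignment, so the problem would probably surface during accrual, under the twice-yearly safety board review.

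**Conclusion.** The point holds as a defect in how the phase I result is concluded and labelled. When true toxicity is clearly below the design curve, the stated rule reports Level 9 as the 0.20 dose in about 92-93% of trials at 0.75x and 99-100% at half or less, with estimates near 0.15, 0.10 or lower. The protocol's own prior gives 40% probability to P(DLT) at Level 9 being below 0.15.

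The simulated figures assume a flat hazard, 75 fully followed patients entering at 2 per month, and true curves proportional to the design curve (or flat at 5%). The result on the model curve needs none of these. The point should be corrected, but it does not threaten the conduct of the trial: nothing here bears on patient safety, dose assignment or the phase II estimate.

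**What to change.** These are reporting changes only; dose assignment stays as written.

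- In Section 13.5.1.1, state that when Level 9 is selected and its 95% posterior interval for P(DLT) lies wholly below 0.20, the result is reported as 'MTD not reached; highest dose level studied'.
- Whenever Level 9 is selected, report its estimated P(DLT) and interval with the label.
- State the matching outcome, 'no level met the target', when the estimated P(DLT) at Level 1 exceeds 0.20.
- In Sections 13.1.2 and 13.5.1.2, name the phase II dose as the MTD, or the highest level studied if the MTD is not reached.
- Add one less toxic scenario to Table 13.1 and report how often each outcome occurs.

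The cost is a few sentences and one simulation scenario, with no added patients and a possibly less definitive headline. The flag's limits should be stated. It is conservative, firing in about 18-19% of trials at 0.75x and 63-67% at 0.5x. On the tabulated run, 91.6 - 19.2 = 72.4% of trials at 0.75x would still carry the MTD label, which is why the estimate and interval should always accompany it. It would also withhold the label in about 4-5% of trials when the design curve is true.

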### **13.3 Sample Size (8/20/10)**

This trial will accrue 75 patients fully evaluable for the DLT toxicity analysis.

Monte Carlo simulation was used to assess the operating characteristics of this design. Complete trials (2,250 for each trial scenario considered) were simulated using 3 different assumptions about the true probabilities of dose-limiting toxicity at each dose: 1) as assumed; 2) somewhat more toxic than assumed; 3) more toxic than assumed with significant increase in toxicity between doses 6 and 7. Among the operating characteristics considered in the sample size were the expected number of dose-limiting toxicities, the probability of selecting the correct dose (that associated with a 20% probability of DLT) as the target dose at the end of the trial, the time required to complete the trial, and the number of patients treated at or near the target dose. Sample sizes from 30 to 120 were evaluated, as were different rates of patient accrual. A sample size of 75 patients was determined to have acceptable probability of correctly selecting a dose with acceptable toxicity and enough patients treated about the target dose for characterization of the efficacy endpoints, while being feasible for completion of accrual within 4 years.

A patient is fully evaluable for toxicity analysis if:

1. The patient fails to complete treatment due to a DLT.  
OR
2. The patient receives all five RT fractions of the protocol treatment.  
AND
  - A. Experiences a DLT within 1 year from the initiation of treatment  
OR
  - B. Is observed per protocol for 1 year after the initiation of treatment and does not experience a DLT

Patients who complete protocol treatment but have progressive disease and no DLT within 1 year are still considered at risk for a DLT even if they receive chemotherapy. It is not likely that the addition of chemotherapy will greatly affect the occurrence of a SBRT-related DLT, and we did not want to exclude patients at risk of DLT.

A patient who does not complete protocol treatment because of non-protocol, treatment-related toxicity; non-protocol, treatment-related death; or refusal to complete protocol treatment will not be evaluable.

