### **13.4 Allocation of Participants to Doses**

#### **13.4.1 The Weighted Dose-Toxicity Model**

Doses will be allocated to patients by means of the Time-to-Event Continual Reassessment Method (TITE-CRM) Phase I trial. A logistic dose-toxicity model was used for this trial with rescaled dose  $d = (\log(p_0 / (1-p_0)) - 3)$ .

$$p(d) = e^{3+ad} / (1 + e^{3+ad}), \text{ (eq. 1)}$$

In the logistic dose-toxicity model, the prior distribution of the dose-toxicity parameter  $\alpha$  is Gaussian with mean 1 and standard deviation of 0.3 which is based upon experience with other trials using this model.  $\alpha=1.0$  represents our initial assumption about the toxicity of treatment, as displayed in the third column of Table 13.1

The weight function reflects the amount of information available from a patient. If a DLT is observed, the full information from this patient is available and the weight will be 1. Otherwise, the uniform weight function ranging from 0 to 12 months will be used. Each patient will be followed for DLT until the patient either reaches one year (12 months) from the start of SBRT without experiencing a DLT or experiences a DLT, whichever comes first. Let the time to a DLT of patient be  $U_i$ , then the weight function,  $w(u) = u/12$ .

This is translated into the following:

- A) Patients who have enrolled in this trial but have not experienced a DLT have a weight equal to the proportion of the 12 months observation period they have completed.
- B) Patients who have experienced a DLT before 12 months from the start of SBRT or complete protocol treatment without a DLT have a full weight, 1.

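### The final 95% intervals for P(DLT) come from a one-parameter curve that cannot fit the protocol's own DLT+ and DLT++ scenarios, so they under-cover away from the working dose, mainly above the MTD

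*Protocol*

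**What the plan says.** Section 13.4.1 of the protocol introduces the model: "A logistic dose-toxicity model was used for this trial with rescaled dose", d = logit(p0) - 3, with logit p(d) = 3 + alpha × d (eq. 1). The prior for alpha "is Gaussian with mean 1 and standard deviation of 0.3 which is based upon experience with other trials using this model". Setting alpha = 1 returns the design column of Table 13.1.

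Section 13.5.1.1 uses the same model for the phase I result: "Markov Chain Monte Carlo will be used to estimate the probability of DLT at each dose, along with 95% posterior intervals". It does not restrict which doses receive an interval. It also asks for the observed proportion with a DLT, and for counts of evaluable patients and DLTs by assigned and by delivered dose, but attaches no interval to them.

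Sections 13.2 and 13.3 test the design under DLT+ (about twice as toxic as assumed) and DLT++, of which Section 13.2 says: "Scenario 3 is more than twice as toxic as the trial design, with rapidly increasing toxicity at dose Levels 7 and higher". The characteristics reported are DLT counts, dose selection, allocation, trial duration and power. Interval coverage is not among them.

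**The concern.** A one-parameter curve is a sound tool for choosing the next dose, because it only has to be right near the target rate. Reporting P(DLT) with a 95% interval at all nine levels asks more of it. Once the data near the working dose have fixed alpha, the skeleton p0 determines every other level. The interval carries uncertainty in alpha but none about the shape of the curve. If true toxicity rises faster than the skeleton, the interval above the MTD is both too low and too narrow.

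At stake is what a reader takes from the reported curve. Someone judging toxicity one or two levels above the MTD would see it understated, with more precision than the data support.

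**Working it through.** **Inputs.** Eq. 1 and the prior (13.4.1); Table 13.1; weight u/12; start at Level 5, highest level with estimated P(DLT) at most 0.20, one level up at a time, 12 cumulative months before escalation (13.4.2); 75 evaluable patients and 2 per month (13.3). The early and late hazard shapes are in a figure that is not available, so Beta(1,3) and Beta(3,1) over 12 months were assumed.

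**Reproducing the protocol's figures.** 75 / 0.80 = 93.75, hence 94 entered, as stated. With 2,000 simulated trials for each scenario and hazard, median DLTs are 10-19 (stated 11-18). Under DLT+, Level 6 is selected in 41-46% (stated about 40%), and the selection is within one level of target in 92-94% (stated over 90%).

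**A check without simulation.** The alpha that reproduces a true probability T at level k is (logit T - 3) / d_k.
- DLT-td: 1.00 at every level.
- DLT+: 0.91 at Level 1; Level 9 is (-0.201 - 3) / (-4.386) = 0.73.
- DLT++: 0.91 at Level 1; Level 9 is (1.386 - 3) / (-4.386) = 0.37.

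No single alpha fits DLT+ or DLT++. Suppose alpha is chosen to be exactly right at the target:
- DLT++, Level 5 (0.18): alpha = (-1.516 - 3) / (-5.442) = 0.830. Eq. 1 then gives Level 7 = 0.27 (true 0.40), Level 8 = 0.31 (true 0.60), Level 9 = 0.35 (true 0.80).
- DLT+, Level 6 (0.20): alpha = (-1.386 - 3) / (-5.197) = 0.844. Level 9 is then 0.33 (true 0.45).

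**Miss rate of the 95% interval** (equal-tailed posterior; range over three hazards, 2,000 trials each):

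| Level | DLT-td | DLT+ | DLT++ |
|---|---|---|---|
| 1-3 | 4-5% | 4-42%, too high | 6-77%, too high |
| 4-5 | 4-5% | 1-7% | 1-19% |
| 6 | 4-5% | 1-2% | 3-21% |
| 7 | 4-5% | 4-13% | 18-61% |
| 8 | 4-5% | 7-19%, too low | 99.7-100%, too low |
| 9 | 4-5% | 49-73%, too low | 99.7-100%, too low |
| Declared MTD | not tabulated | 10-15% | 14-22% |

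**Flat hazard only, 250 trials per scenario.** The declared MTD is missed in 9-11%. The interval one level above the MTD is too low in 11% (DLT+) and 26% (DLT++). Level 9 under DLT+ is missed in 66%, and Level 7 under DLT++ in 44%. At 10%, the simulation error with 250 trials is √(0.1 × 0.9 / 250) = 1.9 percentage points. A further flat-hazard run of 2,000 trials gave 9% and 14% at the MTD and 10% and 29% one level above, so the DLT++ figures could be a few points higher than those from 250 trials.

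**Cause.** Widening the prior SD from 0.3 to 3 leaves DLT+ Level 9 missed in 57% and DLT++ Levels 8-9 in 100%. The fixed intercept is responsible, not the prior.

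**Alternatives on the same kind of trials (flat hazard).** A two-parameter logistic, logit p = c + b × logit(p0) with c ~ N(0, 1.5) and log b ~ N(0, 0.7), cuts the too-low rate one level above the MTD from 11% to 2% (DLT+) and from 26% to 6% (DLT++). It still misses DLT++ Level 8 in 62% and Level 9 in 99%. Under two other prior choices those become 10-19% and 39-68%. Level-specific Jeffreys intervals miss about 5-7% at the MTD and about 3-7% at treated Levels 5-9.

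**The case against.** The phase I endpoint is the MTD, not the whole curve, and carrying the design model into the final analysis is coherent. Coverage is nominal under the protocol's own assumption. At the declared MTD the estimate is nearly unbiased with a flat hazard (mean error below 0.02 in size). Misses there arise almost entirely when a level away from the true target was chosen: under DLT+, none when Level 5 or 6 is selected. The worst figures are extrapolation: with a flat hazard, Level 9 has no patients in 92% of DLT++ trials and 76% of DLT+ trials, and Level 8 has none in 66% of DLT++ trials. The counts already required by 13.5.1.1 would show this. Supplementary intervals could also be left to an SAP.

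Much of this stands. A reader might infer that the intervals fail at every dose, that toxicity is systematically understated at the MTD itself, or that the wrong dose would be chosen. The documents and calculations support none of these. Levels 4-6 under DLT+ are adequately covered, misses at Levels 1-3 run too high, and selection within one level of target holds up.

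What does not fall away is that the protocol itself, not a later plan, names the model, the 95% level and every dose. The upper levels are also not hypothetical: Section 13.2.3 expects on average 8-14 patients (DLT+) or 8-15 (DLT++) at levels with P(DLT) above 0.3. A count of zero beside a narrow interval still invites reliance on the interval.

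**Conclusion.** The point holds in limited form. The final intervals are sound if the design curve is right, and under-cover away from the working dose if toxicity rises as in DLT+ or DLT++. The excess is moderate at the declared MTD: 9-11% with a flat hazard in the 250-trial run, and 10-22% across hazard shapes in the larger one. One level above, the interval is too low in about 11% (DLT+) and 26% (DLT++) of trials. The failure is severe at Level 9 under DLT+ (about two thirds missed) and nearly total at Levels 8-9 under DLT++, always too low, mostly where few or no patients were treated.

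This rests on the assumed early and late hazard shapes, on Poisson accrual (fixed spacing gave a similar result), and on 75 fully evaluable patients without the partly weighted extras that Section 13.3 allows. The flat-hazard results need no assumed shape and show the same pattern.

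**What to change.** Leave eq. 1 in place for dose assignment and MTD selection. In Section 13.5.1.1:

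- (a) Add to the counts already tabulated a level-specific exact or Jeffreys 95% interval for the DLT proportion at each treated level.
- (b) Give no model-based interval for a level at which nobody was treated, or mark it plainly as extrapolation from the assumed curve.
- (c) Beside the eq. 1 intervals, report those from a two-parameter logistic model with free intercept and slope, with priors stated in advance.

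The cross-reference for eq. 1 in that section should also point to 13.4.1 rather than 13.5.1.

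The cost is analysis wording and one extra model fit, with no change to enrolment, dosing or sample size. The two-parameter intervals are about 10% wider at the MTD (for example 0.182 to 0.199, a ratio of 1.09) but roughly 70-95% wider at Level 9. With other priors they are more than double there: under DLT+, from 0.23-0.44 to 0.22-0.66 or 0.22-0.72. Their results depend on the priors, and they do not repair Levels 8-9 under DLT++. That is why (a) and (b) are the core of the change and (c) is supplementary.
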